5.5.2 Scoring of 25FWT

The 25FWT is a quantitative mobility and leg function performance test based on a timed 25-foot walk. The participant is directed to one end of a clearly marked 25-foot course and is instructed to walk 25 feet as quickly as possible, but safely. The time is calculated from the initiation of the instruction to start and ends when the participant has reached the 25-foot mark. The task is immediately administered again by having the participant walk back the same distance. Participants may use assistive devices when doing this task.

The 25FWT score is defined as the average of two trials.

In case a participant needs more than 3 minutes to complete a single trial (or was unable to complete trial due to physical limitations), the maximal time of 3 minutes (180 seconds) will be assigned.

Investigators will be reminded that missing data should be avoided. However, in case only 1 trial was done for other reason than inability to complete the test, the average of the two trials will be replaced by the time for the available trial.

A higher value on the 25FWT is indicative of higher disability.

5.5.3 Scoring of FARS

The FARS-neuro includes 23 items, each item being scored as shown in [Table 15](#). Increments of 0.5 may be used if examiner feels an item falls between 2 defined severities).

The FARS-neuro is a PerfRO, composed of 4 sections that assess different neurological faculties: bulbar activity (4 items), upper limb coordination (5 items assessed right and left side), lower limb coordination (2 items assessed right and left side), peripheral nervous system (5 items assessed right and left side) and upright stability (7 items).

The FARS-neuro is defined as the sum of the different items. The total score varies from 0 to 117. A higher value is indicative of higher disability.

Table 15 - Scoring of neurological examination of the FARS (FARS-neuro)

Section	Item	Range of score
Bulbar	Facial Atrophy, Fasciculation, Action Myoclonus, and Weakness	0-3
	Tongue Atrophy, Fasciculation, Action Myoclonus and Weakness	0-3
	Cough	0-2
	Spontaneous Speech	0-3
Upper limb coordination	Finger to Finger Test – Right and left side	0-3
	Nose-Finger Test - Right and left side	0-4
	Dysmetria - Right and left side	0-4
	Rapid Alternating Movements of Hands – Right and left side	0-3
	Finger Taps - Right and left side	0-4
Lower limb coordination	Heel Along Shin Slide - Right and left side	0-4
	Heel-to-Shin Tap – Right and left side	0-4
Peripheral nervous system	Muscle Atrophy – Right and left side	0-2
	Muscle Weakness – Right and left side	0-5
	Vibratory Sense - Right and left side	0-2
	Position Sense - Right and left side	0-2
	DTR – Right and left side	0-2
Upright stability	Sitting Posture	0-4
	Stance feet apart	0-4
	Stance - Feet Together	0-4
	Tandem Stance	0-4
	Stance on Dominant Foot	0-4
	Tandem Walk	0-3
	Gait	0-5

The activities of daily living score of the FARS includes 9 items, each item being scored as shown in [Table 16](#). Increments of 0.5 may be used if examiner feels an item falls between 2 defined severities).

The activities of daily living score of the FARS is defined as the sum of the different items. The total score varies from 0 to 36. A higher value is indicative of higher disability.

Table 16 - Scoring of activities of daily living of the FARS

Section	Item	Range of score
Activities of daily living	Speech	0-4
	Swallowing	0-4
	Cutting Food and Handling Utensils	0-4
	Dressing	0-4
	Personal Hygiene	0-4
	Falling	0-4

Section	Item	Range of score
	Walking	0-4
	Quality of Sitting Position	0-4
	Bladder Function	0-4

For each section, the score is calculated as the sum of the scores on the items of the section. In case up to 25% of items are missing, a prorated score will be calculated, defined as:

[figure not shown]
$$\text{Score} = \text{Sum of scores of non-missing items} \times \frac{\text{Maximal score if no item is missing}}{\text{Sum of maximum scores of non-missing items}}$$

Maximal number of allowable missing items and maximal score if no item is missing for each section is presented in [Table 17](#).

Table 17 - Maximal number of allowable missing items to calculate FARS scores

Section	Number of items	Maximal number of allowable missing items to calculate score	Maximal score if no item is missing
I. Functional staging of ataxia	1	0	6
II. Activities of daily living	9	2	36
III. Neurological examination			
A. Bulbar	4	1	11
B. Upper limb coordination	10	2	36
C. Lower limb coordination	4	1	16
D. Peripheral nervous system	10	2	26
E. Upright stability	7	1	28
Total neurological examination	35	8	117

5.5.4 [REDACTED]

5.5.5

[REDACTED]

[REDACTED]

[REDACTED]

5.5.6 [REDACTED]

[REDACTED]

Table 18 - [REDACTED]

[REDACTED]

Table 19 -

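### The FARS-neuro total can be prorated with the whole upright-stability section missing, so lost function may read as improvement

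*SAP*

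**What the plan says.** SAP 5.5.3 lists 23 FARS-neuro items. Counting right and left sides separately, Table 17 has 35. On the total, the SAP states: "The FARS-neuro is defined as the sum of the different items". It adds: "The total score varies from 0 to 117. A higher value is indicative of higher disability".

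On missing items the rule is: "In case up to 25% of items are missing, a prorated score will be calculated". The prorated score is the observed sum, multiplied by the full maximum and divided by the maximum of the items observed.

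The limits are in Table 17, headed "Maximal number of allowable missing items to calculate FARS scores". Its columns are number of items, number allowed missing and maximum score. Two rows matter here:

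- "Total neurological examination 35 8 117"
- "E. Upright stability 7 1 28"

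No sentence says that a section's limit also binds the total.

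The timed tests are handled differently. In SAP 5.5.2, a participant who exceeds the time limit on the 25FWT "or was unable to complete trial due to physical limitations" is given 180 seconds. SAP 5.5.1 has the parallel rule of 300 seconds for the 9-HPT. The FARS scoring text has no rule that separates inability from other reasons for a missing item.

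FARS-neuro is one of three secondary endpoints in the primary population (SAP 3.3.1.1). They are tested by the Hochberg procedure once both co-primary endpoints are significant (SAP 3.5). FARS-neuro is analysed as a slope on the untransformed score (SAP 3.3.1.2.3).

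**The concern.** Proration assumes that the missing items would have scored at the same fraction of their maximum as the observed ones. That is tolerable for a scattered missing item. It is not safe when the missing items are a block that measures one function and are missing because that function has gone. Table 17 treats two missing upright items as too many for the section's own score, yet lets seven be missing in the endpoint that is tested.

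The situation is foreseeable. Randomization is stratified on ability to walk, and Protocol 3.1 notes that about 21% of the natural history cohort used a wheelchair. If a participant loses the ability to stand or walk during the trial and the items are left blank, the calculated score can fall while the true score rises. The same score feeds the time-to-worsening and time-to-improvement analyses (SAP 3.3.1.4) and the baseline subgroup split at 50 (SAP 3.2.3).

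**Working it through.** **Inputs.** Item ranges are from SAP Table 15, and limits and maxima from Table 17. S is the observed score on the 28 non-upright items (0 to 89) and U is the true upright score (0 to 28). The documents give neither S nor U, so ranges are shown.

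**1. Reproduce Table 17.** Summing the Table 15 maxima gives:

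- bulbar 11
- upper limb 36
- lower limb 16
- peripheral nervous system 26
- upright 28

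The total is 117 and the item count is 4 + 10 + 4 + 10 + 7 = 35. The limits are 25% rounded down: 0.25 × 35 = 8.75 gives 8, and 0.25 × 7 = 1.75 gives 1. All the neurological rows reproduce.

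**2. Is the total limit a separate rule?** The section limits sum to 1 + 2 + 1 + 2 + 1 = 7, but the total allows 8. A total with eight items missing must therefore break at least one section limit. So the 8 comes from applying 25% to all 35 items, not from the section limits. Seven missing upright items are 7/35 = 20%, which is within the total limit.

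**3. Error with all seven upright items missing.** Prorated total = S × 117/89 = 1.315 × S. True total = S + U. Error = S × 28/89 − U.

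| S | U | True total | Prorated | Error |
|---|---|---|---|---|
| 0 | 28 | 28 | 0.0 | −28.0 |
| 20 | 28 | 48 | 26.3 | −21.7 |
| 35 | 28 | 63 | 46.0 | −17.0 |
| 60 | 28 | 88 | 78.9 | −9.1 |
| 89 | 28 | 117 | 117.0 | 0.0 |
| 89 | 0 | 89 | 117.0 | +28.0 |

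The error is upward whenever U is below S × 28/89.

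**4. Six items missing.** Sitting Posture (0 to 4) needs no standing. If it is scored at 4 and the other six upright items are blank, the observed maximum is 89 + 4 = 93. With S = 35, the prorated total is 39 × 117/93 = 49.1 against a true 63, an error of −13.9.

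**5. Worsening shown as improvement.** Hold S at 35 and let U go from 14 (all items scored) to 28 (items now blank). The true total goes from 49 to 63, a worsening of 14.

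- Seven blank: 46.0, an apparent change of −3.0. A drop appears whenever the earlier U exceeded 46.0 − 35 = 11.0.
- Six blank: 49.1, an apparent change of about 0. A drop appears whenever the earlier U exceeded 49.1 − 35 = 14.1.

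**6. Effect on one participant's slope.** The times in the SAP simulation code are 0, 0.25, 0.5, 1, 1.5 and 2 years, with mean 0.875 and centred sum of squares 2.96875. An error of −17 at Week 104 alone moves that participant's least-squares slope by −17 × (2 − 0.875)/2.96875 = −6.4 points per year.

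**7. Missing at every visit.** If all seven items are blank throughout, the total is 1.315 × S at each visit. The slope on the other items is rescaled, and no false drop appears.

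**The case against.** The strongest objection is that the mechanism is not shown. Bias from lost function needs inability to be recorded as a missing item.

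- **Entry criteria.** Exclusion criterion E 02 removes primary-population participants who cannot perform the study assessments, with exceptions only for the 25FWT and PROs. Non-walkers are nevertheless enrolled. That suggests stance and gait items can be rated in someone who cannot walk.
- **Type of scale.** FARS items are bounded examiner ratings, whereas timed tests need an assigned ceiling. The top category may already mean unable. The anchors are not in the documents, and Protocol 8.1.3 refers details to the study reference manual.
- **Safeguards.** The plan switches to a robust ANCOVA for outlying slopes, includes an MMRM sensitivity analysis, and counts non-completed assessments by visit. FARS-neuro is tested only after both co-primary endpoints succeed.

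The first two points stand as limits on how likely the problem is. They do not settle it: E 02 is an entry criterion and says nothing about how a later loss is recorded. The SAP states an inability rule for the two timed tests, although the protocol refers their details to the same manual. The safeguards may limit the weight of a few distorted slopes, but none corrects the item scoring.

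Two stronger readings are tempting. A reader might infer that the rule favours venglustat. The documents do not support that: the bias favours whichever arm loses more function, and if the drug works that arm is placebo. A reader might also take 17 points as the maximum error. It is one illustration, at S = 35 and U = 28, and proration can also raise the score.

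**Conclusion.** The point holds as a defect in a stated scoring rule. As written, SAP 5.5.3 and Table 17 yield a FARS-neuro total when an entire 28-point section is absent, although that section's own score would not be calculable.

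The arithmetic range of the error with all seven items missing is −28 to +28, with the extremes only at implausible score patterns. With moderate impairment elsewhere (S = 35) and maximal upright impairment, it is −17 with seven items blank. It is about −14 in the more plausible case of six blank items and Sitting Posture at 4.

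The harm is conditional on two things: items scored at earlier visits and blank later, and blanks that reflect lost function. The documents give no frequency for either, so the effect on the treatment comparison cannot be sized. Since this is a multiplicity-controlled endpoint and a better rule can be built from limits already in Table 17, it should be corrected before unblinding.

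**What to change.** In SAP 5.5.3, make two changes together.

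1. Define the FARS-neuro total as the sum of the five section scores, each prorated under its own Table 17 limit. Set the total to missing if any section is not calculable, and remove the separate allowance of 8 for the total.
2. State that an item not done because of physical inability is not treated as missing and takes its worst category, in line with the 9-HPT and 25FWT rules. Check this first against the scale's own anchors and the study reference manual.

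The second change is needed with the first; otherwise lost function would become a missing total. With both in place, the example of S = 35 and inability on all upright items scores 35 + 28 = 63, not 46.

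The cost is SAP wording, scoring reprogramming and probably a few more missing totals. The documents give no basis for estimating how many.

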5.6 APPENDIX 6 STATISTICAL TECHNICAL DETAILS

5.6.1 Criteria for using robust ANCOVA

The procedure to detect outliers will be based on the robust regression with Huber M estimation. The procedure will slightly differ for CSF GM2 (with a single measurement) and for 9-HPT, 25FWT and FARS-neuro (with repeated measurements, analyzed using a slope analysis).

5.6.1.1 Criterion for CSF GM2

Potential outliers will be identified from the standardized residuals, estimated from a robust ANCOVA of percent change in CSF GM2 from baseline to Week 104, with treatment effect (venglustat versus placebo) as factor and the continuous fixed covariate of baseline value.

The robust ANCOVA will be used as primary analysis for the percent change in CSF GM2

5.6.1.2 Criteria for 9-HPT, 25FWT and FARS-neuro

Potential outliers will be identified from the weighted standardized residuals, estimated from a robust ANCOVA on individual slopes, with treatment effect (venglustat versus placebo) as factor and the continuous fixed covariate of baseline value.

The robust ANCOVA will be used as primary analysis for the slope analysis

5.6.2 Confidence interval for the difference in annualized rate of change in 9-HPT

The estimated difference in annualized rate of change in 9-HPT is defined as:

$$\hat{\delta} = \exp(\widehat{\beta_1}) - \exp(\widehat{\beta_0})$$

where $\widehat{\beta}_1$ and $\widehat{\beta}_0$ are the estimated slopes of log-transformed 9-HPT, for the venglustat and placebo arm respectively.

Using the properties of the log-normal distribution, it can be shown that $\exp(\hat{\beta}_l)$ have mean and variance m_i and v_i respectively, equal to:

$$m_i = \exp\left(\widehat{\beta}_l + \frac{Var(\widehat{\beta}_l)}{2}\right)$$

The 90% confidence interval of the difference in annualized rate of change in 9-HPT can be calculated as:

$$m_1 - m_0 \pm z_{0.95} \times \sqrt{v_1 + v_0}$$

where $z_{0.95}$ is the 95th quantile of the normal distribution.

5.6.3 Simulations

5.6.3.1 *Method*

Property of the Sanofi group - strictly confidential

Property of the Sanofi group - strictly confidential

Page 71

5.6.3.2 *Results of simulations*

[figure not shown]

Table 20 - Power: Probability of detecting a difference in slopes under the hypothesis $\delta = -0.0374$

[figure not shown]
A large black rectangular redaction box covering the majority of the page content below the caption.

Table 21 - Type I error: Probability of detecting a difference in slopes under the hypothesis $\delta = 0$

[figure not shown]
A large black rectangular redaction box covering the majority of the page content below the caption.

Table 22 - Root mean squared error (rMSE) for the estimated difference in slopes

[figure not shown]

Table 23 - Hybrid approach: probability of using the robust ANCOVA, under the different scenarios

5.6.3.3 SAS code used to conduct the simulations

```

/*****************************;
/* STEP 1 : Definition of simulation parameters */;
/*****************************;

* Number of simulations;
%let Nsim = 10;

* Total number of patients on venglustat and placebo;
%let NpatV = 38;
%let NpatP = 19;

* List of time-points (in years) ;
%let listtime = 0,0.25,0.50,1,1.50,2.0;

* Seed of simulations ;
%let seed = 15299;

* Drop out rate (at time tdrop) ;
%let rdrop = 0.1;

```

```
%let tdrop = 2;

* Mean and SD of intercept ;
%let mI = 3.5551;
%let sdI = 0.4841;

* Mean slopes on Placebo ;
%let mS_P = 0.0273;

* SD of random slopes (between subject SD) ;
%let sdS = 0.0192;

* SD of residual error (within subject SD) ;
%let sdR = 0.0791;

* Scenarios for the difference in slope (list separated by commas);
%let diff = -0.0374,0;

* Number of scenarios for extreme values;
%let Nsce = 10;

* Base scenario (protocol assumption, no extreme patient ;
%let pE1 = 0;
%let mE1 = 0;
%let sE1 = 1;

* Scenario with 1% extreme patients having mean slope = 0.4;
%let pE2 = 0.01;
%let mE2 = 0.4;
%let sE2 = 0.0192;

* Scenario with 1% extreme patients having mean slope = 0.7;
%let pE3 = 0.01;
%let mE3 = 0.7;
%let sE3 = 0.0192;

* Scenario with 1% extreme patients having mean slope = 0.9;
%let pE4 = 0.01;
%let mE4 = 0.9;
%let sE4 = 0.0192;

* Scenario with 2% extreme patients having mean slope = 0.4;
%let pE5 = 0.02;
%let mE5 = 0.4;
%let sE5 = 0.0192;

* Scenario with 2% extreme patients having mean slope = 0.7;
%let pE6 = 0.02;
%let mE6 = 0.7;
%let sE6 = 0.0192;

* Scenario with 2% patients having mean slope = 0.9;
%let pE7 = 0.02;
%let mE7 = 0.9;
%let sE7 = 0.0192;
```

```
* Scenario with 5% extreme patients having mean slope = 0.4;
%let pE8 = 0.05;
%let mE8 = 0.4;
%let sE8 = 0.0192;

* Scenario with 5% extreme patients having mean slope = 0.7;
%let pE9 = 0.05;
%let mE9 = 0.7;
%let sE9 = 0.0192;

* Scenario with 5% extreme patients having mean slope = 0.9;
%let pE10 = 0.05;
%let mE10 = 0.9;
%let sE10 = 0.0192;
/*********************************************************************
/* STEP 2 : Simulation of clinical trial data under different scenarios */
/********************************************************************

/* Simulation of clinical trial data */
data SimData(keep=diff sce pE mE sE sim subject group base time log9hpt);
length diff sce pE mE sE sim subject group base time log9hpt 8;

retain seed &seed;

* Assess different scenarios for difference and extreme patients ;
do diff = &diff;
do sce = 1 to &Nsce;

  * Get proportion of extreme patients in the current scenario ;
  pE = input(symget("pE"||compress(put(sce,best.))),best.);

  * Get mean slope of placebo for extreme patients in the current scenario ;
  mE = input(symget("mE"||compress(put(sce,best.))),best.);

  * Get SD of slope for extreme patients in the current scenario ;
  sE = input(symget("sE"||compress(put(sce,best.))),best.);

  * Generate simulated clinical trial data for the current scenario;
  do sim=1 to &Nsim;
  do subject = 1 to &NpatV+&NpatP;

    * Assign patients to venglustat or placebo arm ;
    if subject <= &NpatV then group = 1;
    else group = 0;

    * Randomly determine if patient is normal or extreme, and determine mean
    and SD of slope of this patient ;
    call ranuni(seed,u);
    if u > pE then do; mS = &ms_P + group*diff; sdS = &sdS; end;
    if u < pE then do; mS = mE + group*diff; sdS = sE; end;

    * Simulate time to dropout (assuming exponential time to drop-out and
    rate at time &tdrop is &rdrop) ;
    call ranuni(seed,x);
    tdrop = log(x)*&tdrop/log(1-&rdrop);

  end;
  end;

  * Output simulated data ;
  output;
end;
end;
```

```
* Generate a random intercept for the current patient ;
call rannor(seed,int);
int = &mI + int*&sdi;

* Generate a random slope for the current patient ;
call rannor(seed,slope);
slope = mS + slope*sds;

* Create observations at each time-point ;
do time=&listtime;

* Generate a residual error for the current observation ;
call rannor(seed,e);
e = &sdR*e;

* Generate a log(9-HPT) measurement at the given time-point ;
log9hpt = int + slope*time + e;

* Baseline value;
if time = 0 then base = log9hpt;

* Keep only observations before patient drops out ;
if time<tdrop then output;
end;

end;
end;

end;
end;
run;

/* Calculate number observations per subject */
proc means data=SimData nopolish nway;
class diff sce pE mE sE sim subject;
var log9hpt;
output out=nobs(keep=diff sce pE mE sE sim subject nobs) n=nobs;
run;
data Simdata;
merge simdata nobs;
by diff sce pE mE sE sim subject;
run;

/* Calculate individual slopes (for patients with at least 2 observations) */
ods listing close;
options nonotes;
proc mixed data=SimData;
where nobs >= 2;
by diff sce pE mE sE sim subject group base;
model log9hpt = time / s;
ods output solutionF=indSlope(where=(effect="time"))
rename=(estimate=slope));
run;
ods listing;
options notes;
```

```
/* Calculate weights and standardize them (so that mean weight = 1 and sum of
weights = n) */
proc means data=SimData nopolish nway;
  where nobs >= 2;
  class diff sce pE mE sE sim subject group base;
  var time;
  output out=css(keep=diff sce pE mE sE sim subject group base css) css=css;
run;
proc means data=css nopolish nway;
  class diff sce pE mE sE sim;
  var css;
  output out=meancss(keep=diff sce pE mE sE sim meancss) mean=meancss;
run;
data weight;
  merge css meancss;
  by diff sce pE mE sE sim;
  W = css/meancss;
run;

/* Include weights in the simulation dataset */
data indSlope;
  merge indSlope(keep=diff sce pE mE sE sim subject group base slope)
  weight(keep=diff sce pE mE sE sim subject group base w);
  by diff sce pE mE sE sim subject group base;
run;

/* Create observations from both groups, with baseline = mean baseline */
/* In order to obtain predicted mean slope from the PROC ROBUSTREG */
/* (this is because PROC ROBUSTREG has no LSMEANS or ESTIMATE statement) */
proc means data=simdata nopolish nway;
  where time = 0;
  class diff sce pE mE sE sim;
  var base;
  output out=meanbase(keep=diff sce pE mE sE sim base) mean=base;
run;
data pred;
  set meanbase;
  subject = 99.1; group = 0; W=1; output;
  subject = 99.2; group = 1; W=1; output;
run;

/* Include additional observations in the dataset for PROC ROBUSTREG */
data dataRobust;
  set indSlope pred;
run;
proc sort data=dataRobust;
  by diff sce pE mE sE sim subject;
run;

*****/*
/* STEP 3 : Analysis of simulated data with linear mixed-effect model */
*****/

ods listing close;
```

```
options nonotes;

/* Linear mixed-effect model */
proc mixed data=SimData;
  by diff sce pE mE sE sim;
  class subject group;
  model log9hpt = group time group*time;
  random int time / sub=subject type=un;
  estimate "Diff" int 0 group 0 0 time 0 group*time -1 1 / cl;
  ods output estimates=LMMeStimates;
run;

ods listing;
options notes;

/* Get estimate of difference of slopes and calculate 1-sided p-value */
data LMM;
  set LMMeStimates;
  LMMPvalue1S = probt(estimate/stderr,DF);
  keep diff sce pE mE sE sim estimate stderr lower upper LMMPvalue1S;
  rename estimate = LMMEst
        stderr    = LMMSE
        lower     = LMMLower
        upper     = LMMUpper;
run;

*****  
/* STEP 4 : Analysis of simulated data with robust ANCOVA */  
*****  
  
ods listing close;
options nonotes;

proc robustreg data=dataRobust order=data method=M(maxiter=100000);
  by diff sce pE mE sE sim;
  class group;
  id subject;
  model slope = group base;
  weight w;
  ods output ParameterEstimates=RobustParameterEstimates;
  output out=RobustPred predicted=pred stdp=SE sr=stdres;
run;

ods listing;
options notes;

/* Get estimate of difference of slopes and calculate 1-sided p-value */
data Robust;
  set RobustParameterEstimates;
  where parameter = "group" and Level1 = "1";
  RobustPvalue1S = probnorm(estimate/stderr);
  keep diff sce pE mE sE sim estimate stderr lowerCL upperCL RobustPvalue1S;
  rename estimate = RobustEst
        stderr    = RobustSE
        lowerCL   = RobustLower
        upperCL   = RobustUpper;
run;
```

```
run;

/* Calculate number of patients with weighted standardized residual greater
than 3 and greater than 4 */
data outlier;
  set RobustPred;
  where subject notin (99.1,99.2);
  outlier3 = (abs(W*stdres) > 3);
  outlier4 = (abs(W*stdres) > 4);
run;
proc means data=outlier nopolish nway;
  class diff sce pE mE sE sim;
  var outlier3 outlier4;
  output out=Noutlier(keep=diff sce pE mE sE sim nOutlier3 nOutlier4)
sum=nOutlier3 nOutlier4;
run;

/*************************************************/
/* STEP 5 : Combine results and report simulation results */
/*************************************************/

/* Combine results from the linear mixed model and from robust ANCOVA */
data AllResults;
  merge LMM Robust Noutlier;
  by diff sce pE mE sE sim;

  * Hybrid approach: use robust ANCOVA if at least one patient with
  standardized residual > 4 or at least 2 patients with standardized residual >
  3;
  * otherwise, use linear mixed-effect model ;
  if nOutlier4 >= 1 or nOutlier3 >= 2 then do;
    Robust      = 1;
    HybridEst   = RobustEst;
    HybridSE    = RobustSE;
    HybridLower = RobustLower;
    HybridUpper = RobustUpper;
    HybridPvalue1S = RobustPvalue1S;
  end;
  else do;
    Robust      = 0;
    HybridEst   = LMMEst;
    HybridSE    = LMMSE;
    HybridLower = LMMLower;
    HybridUpper = LMMUpper;
    HybridPvalue1S = LMMPvalue1S;
  end;

  * Determine if significant at 0.05 one-sided level ;
  LMMSign    = (LMMPvalue1S < 0.05);
  RobustSign  = (RobustPvalue1S < 0.05);
  HybridSign  = (HybridPvalue1S < 0.05);

  * Coverage of 95% confidence interval ;
  LMMCover   = (LMMLower < diff < LMMUpper);
  RobustCover = (RobustLower < diff < RobustUpper);
  HybridCover = (HybridLower < diff < HybridUpper);
```

```
* Bias in difference ;
LMMBias = LMMEst - diff;
RobustBias = RobustEst - diff;
HybridBias = HybridEst - diff;

* Squared Error ;
LMMBias2 = LMMBias**2;
RobustBias2 = RobustBias**2;
HybridBias2 = HybridBias**2;

run;

/* Calculate simulation results */
proc means data=AllResults noprint nway;
  class diff sce pE mE sE;
  var Robust LMMSign RobustSign HybridSign LMMCover RobustCover HybridCover
LMMBias RobustBias HybridBias LMMBias2 RobustBias2 HybridBias2;
  output out=SimResults(keep=diff sce pE mE sE pRobust LMMPSign RobustpSign
HybridpSign LMMPCover RobustpCover HybridpCover LMMMeanBias RobustMeanBias
HybridMeanBias LMMSE RobustMSE HybridMSE LMMRatepCover RobustRatepCover
HybridRatepCover)
  mean=pRobust LMMPSign RobustpSign HybridpSign LMMPCover RobustpCover
HybridpCover LMMMeanBias RobustMeanBias HybridMeanBias LMMSE RobustMSE
HybridMSE;
run;

/* Prepare dataset for reporting */
data SimResults;
  set SimResults;
  by diff sce pE mE sE;
  retain num 0;
  if first.diff then num = 0;
  if pE ne lag(pE) then num = num + 1;

  if pE = 0 then mE = .;

* Calculate root MSE ;
LMMRMSE = sqrt(LMMSE);
Robustrmse = sqrt(RobustMSE);
Hybridrmse = sqrt(HybridMSE);

run;

/* Report simulation results */
option ps=250 ls=250;

title "Results of simulation, based on &Nsim simulations";

proc report data=SimResults headline headskip nowd split = "@" formchar(2)="-";
  column diff num ("Scenario" "----" pE mE)
    ("Probability of significant@difference of slopes" "----" LMMPSign
RobustpSign HybridpSign)
    ("Coverage of 95% CI@of difference of slopes" "----" LMMPCover
RobustpCover HybridpCover)
```

```
      ("Mean bias in@ difference of slopes" "---" LMMMeanBias
      RobustMeanBias HybridMeanBias)
      ("Root mean squared error in@difference of slopes" "---" LMMRMSE
      RobustRMSE HybridRMSE)
      pRobust
      ;

      define diff           / "Difference"      group center width=10 f=7.4
      order=data;
      define num            / group noprint;
      define pE              / "Proportion of extreme patients" display center
      width=18 f=percent8.0;
      define mE              / "Mean slope in extreme patients" display center
      width=18 f=4.1;
      define LMMpSign        / "LMM"      display center width=8 f=percent8.1;
      define RobustpSign     / "Robust"   display center width=8 f=percent8.1;
      define HybridpSign     / "Hybrid"   display center width=8 f=percent8.1;
      define LMMpCover       / "LMM"      display center width=8 f=percent8.1;
      define RobustpCover    / "Robust"   display center width=8 f=percent8.1;
      define HybridpCover    / "Hybrid"   display center width=8 f=percent8.1;
      define LMMMeanBias    / "LMM"      display center width=8 f=8.5;
      define RobustMeanBias / "Robust"   display center width=8 f=8.5;
      define HybridMeanBias / "Hybrid"   display center width=8 f=8.5;
      define LMMRMSE         / "LMM"      display center width=8 f=8.4;
      define RobustRMSE      / "Robust"   display center width=8 f=8.4;
      define HybridRMSE      / "Hybrid"   display center width=8 f=8.4;
      define pRobust         / "Probability@of using@robust ANCOVA" display center
      width=15 f=percent8.1;

      break after diff / skip;
      break after num / skip;

run;
```

